## **3. STUDY DESIGN**

The time frame for this study will be approximately one month, with the first presentation of the program being in March 2020. This program will be provided to high school and college students within the Dallas Fort Worth metroplex. The program will be implemented by community outreach, as the students will be presented with information about vaping and the resources necessary to prevent or stop vaping from their daily lives. The purpose of this study is to relay and publish data that will support the education of vaping and the many health risks associated with vaping products.

During this program, we will be presenting to 20 to 30 students at a time in a classroom setting, which will allow us to closely interact with participants. This is an anonymous study; therefore, all participants' names will not be listed nor stated in any documentation. In order to accurately complete this anonymously while also calculating our results, students will be asked to list their age, gender, race, and zip code on their survey. This program will be approximately 35 minutes. Participants will be given a pretest (Appendix C) before any information is presented. Students will be given an incentive to complete this program. Below is an outline (Appendix D) of the program:

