Many vaping companies present their products as nicotine free and as being a safe and non-addictive way of smoking. From commercials to online ads, consumers are being told that this product is free from the smell of cigarettes, reusable, much cheaper, and even healthier than traditional cigarettes. This information can be very deceiving and persuasive to the young mind.

This program titled, “To Vape or Not to Vape”, will provide education to adolescents and young adults about the potential risk of vaping in an effort to assist with lowering the usage rates within the population. Content will include information about current statistics, potential short-term and long-term side-effects, and healthy alternatives for dealing with stress and peer-pressure. We anticipate that this program will increase this population’s knowledge about the risks of vaping products, and deter them from future use of the products. Effectiveness of this program will be measured by pre and post-tests.

**1.2.** Aim(s)/Objective(s)

The overall goal of this study is to increase knowledge of vaping and its associated risks. This study will find the patterns of vaping, and how it all started among adolescents. We want to know if students are aware of the serious and long term effects of vaping.

The objectives are:

1. To provide at least 100 middle school and high school students with anti-vaping education.
2. To provide at least 40 college students with anti-vaping education.
3. To improve the overall knowledge of vaping statistics and side effects as measured by a pre and post-test. The pre-test will be the baseline measurement. The post-test will be the measure of effectiveness. Out of the 10 questions on the post-test, the goal is to have the students answer at least 8 out of the 10 questions correctly.
4. To decrease the percentage of students who say that they are likely to vape in the future.

The program will be going to middle school, high school, and college campuses in the Dallas-Fort Worth (DFW) area to speak with students about vaping. The program will be implemented by community outreach, as the students will be presented with information about vaping and the resources necessary to prevent or stop vaping. This program will present the students with a 35-minute curriculum that is listed below. The purpose of this study is to relay

and publish data that will support education about vaping and the many health risks associated with vaping products.

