### **1.4.** Hypothesis

We believe this program will make at least 50 percent of the participants more aware of the dangers and consequences of vaping, potentially lowering the rates of those participating in this habit while also preventing others from starting.

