## 5. STATISTICAL CONSIDERATIONS

## 5.1. Sample Size Considerations

A power analysis using the G-power 3.1 computer program (Faul & Erdfelder, 2009) indicated that a total sample of 35 people would be needed to detect a medium effect (Cohen's  $dz = 0.5$ ) with 80% power using matched-pairs Wilcoxon signed-rank test with alpha at 0.05 and assuming non-normal distribution. We need to enroll at least 44 subjects to account for 20% attrition rate. We plan to enroll 100 subjects in this study from whom we will collect pre- and post-test data on vaping.

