## 5.2. Statistical Analysis Plan

Descriptive analysis will be performed for all continuous variables. Mean  $\pm$  standard deviation will be presented for normally distributed variables and median  $\pm$  interquartile range will be presented for non-normal variables. Count and proportions will be presented for all categorical variables. All normally distributed continuous outcomes will be analyzed with paired t test and non-normally distributed continuous outcomes will be analyzed with nonparametric Wilcoxon signed-rank test. All Categorical outcomes will be analyzed using McNemar test.

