## **6.3. Informed Consent / HIPAA Waiver**

### **Informed Consent**

Study subjects will not be provided an informed consent form due to the study being anonymous and confidential within an educational setting. There are no risk associated with this study and no names or identification will be presented on participants documents. Participants will be asked to state their zip code and grade level on the pre and post-test in order to gather our data. Consent to participate is obtained without coercion or undue influence.

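### Every planned test is paired, but no visible text says how a student's anonymous pre-test is joined to that student's post-test

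*Combined protocol and SAP*

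**What the plan says.** Section 5.1 sizes the study "using matched-pairs Wilcoxon signed-rank test with alpha at 0.05", with dz = 0.5 and 80% power. It needs 35 people, then adds: "We need to enroll at least 44 subjects to account for 20% attrition rate". Planned enrolment is 100. Section 5.2 names three inferential tests, all paired: "All normally distributed continuous outcomes will be analyzed with paired t test", the Wilcoxon signed-rank test for non-normal outcomes, and "All Categorical outcomes will be analyzed using McNemar test".

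No names are recorded (Sections 3, 6.1, 6.3 and 6.4). Two places list what students write on the forms:

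- Section 3: to work "anonymously while also calculating our results, students will be asked to list their age, gender, race, and zip code on their survey".
- Section 6.3: "Participants will be asked to state their zip code and grade level on the pre and post-test in order to gather our data".

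Section 6.4 says that identifiers will be stripped from the collection tools at study close, but defines none. Section 7.4 describes paper forms transferred to Excel, with no linking step. Appendix B has separate headings for the pre-test and post-test spreadsheets, and their columns are not visible. The forms printed in Appendix C show no code and no demographic field.

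**The concern.** A paired test needs each student's own two values. With no names and no stated key, the analyst would have to choose a method after the forms are in: match on demographics and break ties somehow, keep only students with a unique profile, or drop pairing and run a test that the plan does not contain.

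The results at stake are those that compare before with after: the change in understanding (Section 2.2.2), objective 4 in Section 1.2 ("To decrease the percentage of students who say that they are likely to vape in the future"), and one reading of the hypothesis in Section 1.4 ("We believe this program will make at least 50 percent of the participants more aware of the dangers and consequences of vaping"), namely the share of students whose own score rose. McNemar's discordant counts and that per-student share cannot be recovered from unlinked totals, and anonymous forms that were never linked cannot be matched later.

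**Working it through.** **1. The plan's own figure.** Signed-rank power was computed from the noncentral t distribution with effective size n × 3/π, dz = 0.5 and two-sided alpha 0.05. At n = 35 power is 0.801, and at n = 34 it is 0.789. Attrition: 35 / 0.8 = 43.75, so 44. Both stated figures reproduce, and both count complete pairs.

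**2. How well the listed fields identify a student.** Section 3 gives classes of 20 to 30. The documents give no class composition, so every mix here is an assumption. If p is the probability of a profile (the product of the field shares), the expected share of a class of m that is unique is Σ p(1 − p)^(m − 1). Two equal genders are assumed throughout.

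| Key and assumed mix | Unique, m = 25 |
|---|---|
| Four fields, base: 2 equal ages; race 40/30/20/10; zips 50/30/20 | 53% (60% at m = 20, 47% at m = 30) |
| Four fields, homogeneous: ages 90/10; race 70/15/10/5; zips 80/15/5 | 25% |
| Four fields, mixed college: 4 equal ages; race 40/30/20/10; 10 equal zips | 91% |
| Zip in a single-grade class, zips 50/30/20 | 0.1% |
| Zip in a single-grade class, 10 equal zips | 8% (13.5% at m = 20, 4.7% at m = 30) |

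For example, with ten equal zips: 10 × 0.1 × 0.9^24 = 0.080.

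**3. McNemar, illustrated.** The documents give no baseline, target or discordance for likelihood of vaping. Assume a fall from 30% to 15%, with 2% moving the wrong way (p01 = 0.02). Then p10 = 0.30 − 0.15 + 0.02 = 0.17, and 0.19 of students are discordant. If forms were paired wholly at random, p10 = 0.30 × 0.85 = 0.255 and p01 = 0.70 × 0.15 = 0.105, so 0.36 would be discordant. The difference is 0.15 either way. Mis-joining leaves the estimated change intact but adds noise to the test.

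Simulated power of the exact test, base mix, with post-test forms shuffled among students who share a class and key:

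| Students | True linkage | Four fields | Zip + grade |
|---|---|---|---|
| 80 (100 in Section 5.1, less 20%) | 88% | 80% | 60% |
| 112 (100 + 40 in Section 1.2, less 20%) | 97% | 94% | 83% |

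**4. The Wilcoxon test that was sized.** Same shuffling, 80 students, dz = 0.5, pre/post correlation assumed:

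| Correlation | True linkage | Four fields | Zip + grade |
|---|---|---|---|
| 0.5 | 99% | 98% | 94% |
| 0.7 | 99% | 97% | 80% |

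At correlation 0.5 the type I error is 0.049, 0.031 and 0.009 respectively. Shuffling makes the test conservative here; only positive correlations were simulated.

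**5. Per-student change.** Take the eight post-test items other than pressure and likelihood, with pre-test scores Binomial(8, 0.6). If 30% of students gain one point and 15% gain two, 44% truly improve, but zip-plus-grade pairing shows 51%. If 50% and 30% do, a true 79% shows as 63%. The error can go either way.

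**The case against.** The case on the other side has real force in five places.

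- **Section 3 gives the fields a purpose.** Its wording ties the demographic fields to staying anonymous while computing results, and the natural reading is an anonymous key. This stands: on that reading the gap is a missing matching and tie rule plus an inconsistent field list.
- **A code may exist.** Section 6.4 implies that the tools hold some identifier until close, although this may mean only the demographic fields. The Appendix B columns and some pages are not visible. A reader might infer that the study has no linkage at all; the documents do not support that.
- **The two lists may be cumulative.** The zip-plus-grade figures apply only if Section 6.3 replaces Section 3. The Section 3 and 4 tables also use the three-zip mix for that key, the less favourable of the two shown for zip code.
- **Both tests fall within one session of about 35 minutes.** Forms could be stapled, or handed out and collected together. This softens the gap but does not close it, because no such step is described.
- **The McNemar figures rest on assumed inputs.** The test was not sized, and the four-category likelihood item needs a binary cut that the plan does not state. The loss is much smaller at 112 students than at 80.

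A reader might also infer that 35 or 44 is wrong, or that the primary outcome fails. Neither follows. The sample size reproduces. The primary outcome in Section 2.2.1 is taken from the pre-test, and the 8-of-10 goal from the post-test alone. The marginal percentages behind objective 4 can be estimated without linkage; only the planned test of them needs it.

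**Conclusion.** The concern holds as a missing procedure. The plan relies on paired tests throughout, and no visible text says how pairs are formed. The only candidate keys are two different field lists, and neither comes with a rule for ties or inconsistent entries.

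The size depends on assumptions about class mix, correlation and response rates. The four-field key would be unique for about half of a class of 25 (25% to 91%), and zip code within a grade for about 0.1% to 8%. The exposure lies mainly in the McNemar analysis of likelihood of vaping and in any per-student change. For the sized Wilcoxon test at 80 pairs, four-field matching costs one or two points of power. This should be fixed before data collection because the remedy is cheap and the loss could not be repaired afterwards. It does not invalidate the design or the stated sample size.

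**What to change.** Pre-print the same random number, linked to no name, on each student's pre-test and post-test, and hand the two out as one packet. If a code already exists in Appendix B, name it in the protocol instead.

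- In Section 5.2, state that pairs are formed only on that number, and that forms without a partner are counted, reported and left out of the paired tests.
- In Sections 3 and 6.3, use one list of demographic fields.
- In Sections 6.3 and 6.4, say that the anonymous number is permitted.

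The cost is printing a number on two sheets and a short wording change for the IRB. No name is attached at any point, so anonymity is unchanged.

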### 6.4. Participant Confidentiality

Participant confidentiality will be strictly maintained at all times with all information used being non-traceable to the participants. This study will be anonymous as participants names will not be on any documents or test.

Information will only be accessed by the principal investigator or sub-investigators. No identifiable participant data will be disclosed. All information obtained will be source de-identified, presented on a large scale, and not traceable to any one particular individual. All data collected will be kept on the password protected hospital server, and only authorized trained personnel will have access to the share drive. All physical information will be shredded in the lock shred box located in the Cancer Administration Program office. At close of this study, all identifiers will be removed from the data collection tools.

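### Age, gender, race and zip code on forms completed in groups of 20 to 30 could single out many students, which conflicts with the non-traceable and no-risk statements in 6.3 and 6.4

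*Combined protocol and SAP*

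**What the plan says.** Section 3 sets both the items and the group size. It states that "students will be asked to list their age, gender, race, and zip code on their survey" and, of the sessions, "we will be presenting to 20 to 30 students at a time in a classroom setting".

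The Informed Consent text in 6.3 says "There are no risk associated with this study and no names or identification will be presented on participants documents". Its next sentence gives a different list of items: "Participants will be asked to state their zip code and grade level on the pre and post-test". The same paragraph explains the absence of a consent form by the study being anonymous and confidential in an educational setting. The waiver request that follows describes the research as no more than minimal risk.

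Section 6.4 promises "Participant confidentiality will be strictly maintained at all times with all information used being non-traceable to the participants" and gives the basis as "This study will be anonymous as participants names will not be on any documents or test". It also limits access to the investigators, places the data on a password-protected server, and promises large-scale reporting. It ends by saying that identifiers will be taken off the data collection tools when the study closes.

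The pre-test in Appendix C asks about smoking, current vaping, frequency, duration and feeling pressured to vape (items 1 to 4 and 12). Neither form in Appendix C, as reproduced, shows a demographic field. Students aged 12 and over may take part (4.2).

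**The concern.** The evident risk to a participant here is that someone learns that student's answers. A form without a name can still point to one student if its age, gender, race and zip code fit only one person in the room. The promise in 6.4 rests on the absence of names, which does not deal with combinations of other items. Section 6.4 also implies that identifiers stay on the tools until close-out.

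Two things are at stake. Anonymity is half of the reason 6.3 gives for having no consent form, in a study that enrols minors. The primary outcome in 2.2.1, the percentage of vape users, also comes from the same pre-test, so it depends on candid answers.

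**Working it through.** The plan gives no figure for traceability and no class composition. Every class mix below is therefore an assumption, with items treated as independent. The group size of 20 to 30 comes from section 3.

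**Formula.** A student in a cell (one age-gender-race-zip combination) of probability p is unique in a class of n if none of the other n − 1 students falls in that cell. The expected share of unique students is the sum over all cells of p(1 − p)^(n−1).

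**Assumed mixes.**
- Homogeneous: age 85/15, gender 50/50, race 75/15/10, zip 75/15/10 (36 cells).
- Moderate: age 60/40, gender 50/50, race and zip each 50/25/15/10 (64 cells).
- College: four equal ages, gender 50/50, race 40/30/20/10, ten equal zip codes (320 cells).

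**Two cells of the moderate class, n = 25.** The commonest cell has p = 0.6 × 0.5 × 0.5 × 0.5 = 0.075, and a student in it is unique with probability 0.925^24 = 0.15. The rarest has p = 0.4 × 0.5 × 0.1 × 0.1 = 0.002, giving 0.998^24 = 0.95. Weighting all 64 cells by p gives 53%.

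**Expected share unique on all four items.**

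| Class | n = 20 | n = 25 | n = 30 |
|---|---|---|---|
| Homogeneous | 29% | 25% | 22% |
| Moderate | 60% | 53% | 48% |
| College | 93% | 91% | 90% |

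A second set of assumed mixes gives a similar spread, from 19% (single grade, one dominant race, two zip codes, n = 30) to 96% (college, five ages, 15 zip codes, n = 20).

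**Gender and race only, n = 25.** For the moderate class: 2 × [0.25 × 0.75^24 + 0.125 × 0.875^24 + 0.075 × 0.925^24 + 0.05 × 0.95^24] = 0.0005 + 0.0101 + 0.0231 + 0.0292 = 0.063. The other two mixes give 5%. Most of the uniqueness therefore comes from adding age and zip code.

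**The item list in 6.3 instead (zip code and grade level).** In a single-grade class only zip code separates students. The share is about 0% to 4% with 2 to 5 zip codes, and 14% to 27% with 15 equally common ones. The size of the problem therefore depends on which list is used.

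**Possible effect on prevalence.** Reported prevalence = true prevalence × (1 − share of users who deny use). Take the 28% high-school figure in 1.1 as the true value and an assumed denial share of 10% to 25%:
- 28% × 0.90 = 25.2%, a shift of 2.8 points.
- 28% × 0.75 = 21.0%, a shift of 7.0 points.
- 95% half-width at the planned 100 subjects: 1.96 × √(0.28 × 0.72 / 100) = 8.8 points.

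The assumed shift lies within the sampling error, and no denial rate can be derived from the documents.

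**The case against.** The strongest reply is that the plan does more than leave names off. Section 6.4 restricts access and reports in aggregate, 7.1 and 7.2 require locked or password-protected storage, and 7.5 bars sharing outside the study team. A unique combination identifies a student only to someone who both holds the form and knows the class. This stands, and it lowers the chance of disclosure. But these are confidentiality measures. They govern who may see a form, whereas 6.4 claims that the form cannot be traced.

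The variables also have a use. Section 5.2 describes all continuous and categorical variables, which takes in age, gender, race and zip code, and the primary objective in 2.1.1 concerns teens and young adults, so some age information is needed. This stands, and it is why a coarse age band is better than no age item.

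A reader might infer three stronger points that the documents do not support:
- That the forms simply are traceable. Class make-up is unknown, the share varies widely, and the list in 6.3 would identify far fewer students.
- That the prevalence estimate will be pushed down. Nothing shows that students would feel identifiable or would deny use, so this is only a possibility.
- That the case for waiving consent collapses. Section 6.3 relies on confidentiality as well as anonymity, and the listed grounds for the waiver do not include anonymity.

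**Conclusion.** The concern holds in a limited form. With the items in section 3 and groups of 20 to 30, many forms could be singled out by someone who has them and knows the class: about 22% to 93% of students across the three main mixes, against about 5% to 6% with gender and race only in a class of 25. These percentages rest on assumed category frequencies and independence.

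The textual conflict needs no assumption. Non-traceability in 6.4 and the absence of identification in 6.3 do not fit the items requested in section 3, or the statement in 6.4 that identifiers are removed at close. The no-risk sentence in 6.3 also disagrees with the minimal-risk wording of the waiver request. Because minors report vaping and smoking on these forms, the wording and the items should be corrected before the forms are printed.

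**What to change.** 1. Reconcile section 3, 6.3 and Appendix C on which items are collected, and show them on the forms.
2. Replace zip code with a yes/no item on living in the DFW area, which serves the residence criterion.
3. Replace exact age with a coarse band that still checks the 12-or-older criterion and separates teens from young adults.
4. Ask gender and race once, on the pre-test.
5. Link each pre-test to its post-test by a random pre-printed number, with no list tying numbers to students. The plan names no other link, so the demographic items may be serving as the matching key. Removing them without a replacement would break the paired t, Wilcoxon signed-rank and McNemar tests in 5.2.
6. In 6.3 and 6.4, replace the no-risk and non-traceable statements with one that names disclosure of answers as the risk and says how it is limited, in line with the minimal-risk wording of the waiver request.

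The cost is protocol and form wording before printing. Zip-level and exact-age description, which the general descriptive analysis in 5.2 would have covered, is lost.

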## **I. Introduction**

1. Introduce ourselves
2. Present the Pretest

## **II. Thesis statement**

1. Goals and objectives of the study

## **III. Main points**

1. Chemicals that are in vapes
2. The difference between e-cigarettes and vapes
3. Risk and side effects of vaping
4. What happens inside the body when vaping
5. Resources available to help quit and prevent vaping

